1. PROJECT TITLE

Acceptance and Commitment Therapy to Address the Psychosocial Co-Morbidities of Chronic Pain in Aging People Living with HIV

4. ESTIMATED DURATION OF THE STUDY

Training, enrollment and study procedures are projected to last 2 years. This study will be open with IRB for up to 7 years

5. LAY LANGUAGE SUMMARY OR SYNOPSIS

Chronic pain affects a very high proportion of aging people living with HIV (aPLWH) and is thought to be related to both direct toxicity of HIV and antiretroviral therapy (ART) and by psychosocial factors that negatively affect pain (i.e. loneliness, HIV stigma). PLWH are also at increased risk for prescription opiate misuse. However as PLWH age, non-opiate medications used for pain can contribute to other negative outcomes such as falls, altered mental status and gastrointestinal bleeding. Thus there is a critical need for the development of novel interventions in the management of chronic pain in aPLWH that consider the psychological co-morbidities of aging with HIV and that can minimize the need for prescription medications. Acceptance and commitment therapy (ACT) has previously been evaluated in older persons with chronic pain and has demonstrated higher levels of satisfaction and efficacy when compared to cognitive behavioral therapy (CBT). ACT has never been evaluated in aPLWH for chronic pain, but has theoretical advantages over CBT for this population. Specifically several negatively modifying factors of CBT efficacy such as cognitive deficits are common in aPLWH.

6. SPECIFIC AIMS

Aim 1: To determine feasibility of training lay-personnel in the performance of ACT for aPLWH to inform future implementation. Many HIV clinics employ non-medical staff such as case managers and health educators who if trained to provide ACT would expand of ACT access to aPLWH. We will train a substance abuse counselor and case manager in ACT to inform the feasibility of future ACT scale-up efforts.

Aim 2: To conduct an uncontrolled study of group ACT for chronic pain in aPLWH to inform adaption of ACT for aPLWH. Ten aPLWH will participate in 6 weekly sessions of group-administered ACT. Informed by the Method for Program Adaption through Community Engagement (MPACE) Model, I will synthesize and present data from questionnaires, participant feedback and end of study focus group to a steering committee for adaption recommendations(1). These procedures can occur in person or remotely. We will statistically evaluate the process and compare group cohesion scores between persons who attend live and remotely.

Aim 3: To conduct a controlled, two-group, pilot randomized trial of adapted ACT for aPLWH as compared to group education. Forty aPLWH with chronic non-cancer pain will be randomized to 6 weeks of group ACT or group education. Participants will undergo evaluations of acceptability as the primary outcome as recommended by the ORBIT model(2). Additional evaluations will include self-reported pain severity and interference, outcomes of physical performance, and quality of life (3, 4).

The long-term goal of this research is to develop an effective non-pharmacologic intervention to improve chronic pain in aPLWH that can be feasibly implemented on a large scale in HIV clinics. This research, in conjunction with the activities proposed in the Professional Development Plan, will help launch my career as a future leader in aging-focused research.

In order to address these hypotheses and aims, human subjects are required.

7. BACKGROUND AND SIGNIFICANCE

Chronic pain impacts up to 85% of people living with HIV (PLWH) (5-9). The high prevalence is due to direct and indirect effects of HIV (i.e., direct HIV toxicity and secondary toxicity of antiretroviral therapy on the central and peripheral nervous systems(10-13)) and magnified by co-occurring psychosocial factors such as depression (14), stress (15), past trauma (16), social isolation (17), and substance use (18-24). These co-occurring factors also contribute to increased risk for prescription opiate misuse and overdose mortality (25-27) and to maladaptive coping (avoidance, thought suppression, and catastrophizing)(28-32) that negatively modifies the pain experience. As this population ages, the medical management of pain increases in complexity as aging PLWH (aPLWH; ≥ 50 years in the literature) accumulate age-associated painful co-morbidities like osteoarthritis. Additionally, most non-opiate medications used for pain (i.e., skeletal muscle relaxants, NSAIDS) have side effects that increase risks for falls, delirium, and gastrointestinal bleeding that may further worsen the health of aPLWH (33-37). Thus, developing novel interventions that target pain relief and function, consider relevant psychosocial co-morbidities of aging with HIV, and minimize medication use remains a priority.

The biopsychosocial theoretical framework as first proposed in Melzack and Wall's "gate control theory of pain" and represented at the core of our conceptual model (in green in Figure 1) is a well-established, accepted model of pain(38, 39). This framework has influenced the development of several interventions including the self-regulatory approaches of biofeedback and mindfulness-based stress reduction and psychological approaches like cognitive behavioral therapy (CBT) and acceptance and commitment therapy (ACT) (40). CBT, the longest standing psychological approach to pain management, can result in reduced pain, increased function, and decreased disability(41). However, success with CBT requires persons to 1) *understand* that thoughts and behaviors affect the pain experience, 2) *develop* cognitive and behavioral *skills to change* these thoughts and behaviors, and 3) *engage in ongoing work* to manage or reduce pain. Several pre-existing factors such as cognitive deficits or an inability to confront and control complex emotions impair CBT responses (42-44). ACT, on the other hand, recognizes that attempts to forcibly change negative thoughts and longstanding behaviors can be futile and result in increased suffering and distress (45, 46). ACT instead focuses on acceptance of negative feelings while concurrently taking steps towards outcomes that are valued and provide meaning to the individual (47-49). In chronic pain, ACT like CBT also improves pain related

[figure not shown]
factors such as emotional and physical function (50) and demonstrates higher levels of satisfaction as a pain intervention than CBT (51). Of note work by [name] ACT may also be more effective than CBT in older adults (52, 53), while younger persons appear to respond better to CBT. ACT is understudied in HIV and never evaluated for chronic pain, but exhibits a positive impact on HIV stigma(54) and life experiences (55, 56). This approach may be particularly effective in PLWH who demonstrate maladaptive coping such as thought suppression and avoidance due to underlying psychosocial co-morbidities of HIV including HIV stigma, substance use, and past trauma (57-60). Additionally, aPLWH demonstrate high rates of cognitive deficits and are limited in their capacity to change their circumstances (i.e. due to poverty, homelessness) (52, 53) (42-44) both factors that impair CBT response and favor ACT.

The scientific premise of this grant is that chronic pain in aPLWH is caused by the direct effects of HIV and modified by the psychological and social co-morbidities of aging with HIV (See Figure 1. Conceptual Model). Direct HIV effects on the brain (i.e. neurotoxicity of HIV and antiretroviral therapy) and the psychosocial co-morbidities of aging with HIV (past trauma, HIV stigma, perceived stress, loneliness, substance use, mental illness, and social isolation) lead to maladaptive coping (such as catastrophizing) that magnifies pain, impairs cognitive performance, and enhances pain perception. ACT has the potential to positively impact the chronic pain experience (pain, function, and quality of life) in aPLWH by addressing psychosocial co-morbidities and maladaptive coping and is less dependent than CBT on baseline cognitive function and the capacity to change personal circumstances.

Evaluation of new chronic pain strategies for aPLWH remains crucial because this is a steadily growing high need population⁽⁶¹⁾ and chronic pain is a highly prevalent co-morbidity(5-9). Current CDC recommendations for the management of chronic pain are insufficient for aPLWH as these guidelines do not consider the serious side effects of non-opiate pain medications that PLWH are at risk for as they age(37) and the lack of access to non-pharmacologic therapies due to psychosocial circumstances of aPLWH.

ACT versus CBT for chronic pain in older adults: CBT and ACT are effective psychological interventions for chronic pain, and yet demonstrate small to moderate effect sizes(62-65) on pain outcomes. Key medical and psychosocial co-morbidities may influence treatment outcomes and effects, thus adaption of psychological approaches may enhance efficacy at the target population and individual level. In fact, CBT and ACT demonstrate differential effectiveness based on the population in which they are used. [name], a Co-Investigator on this grant, performed an 8-week randomized clinical trial of CBT versus ACT for chronic pain in persons aged 18-89 years in San Diego, and although there were no differences in pain-specific outcomes, ACT participants reported higher levels of satisfaction(51). A

Figure 1 Biopsychosocial Conceptual Model of Chronic Pain adapted for aPLWH

Adapted with permission from Bushnell MC. Nat Rev Neurosci 2013

secondary analysis demonstrated that older participants were more responsive to ACT while younger participants responded better to CBT(52). This difference was present at completion of the intervention and at 6 month follow-up. Several characteristics of aPLWH suggest that ACT may be particularly effective for aPLWH, as previously discussed and represented in the Conceptual Model (Fig 1).

8. PRELIMINARY STUDIES/PROGRESS REPORT

n/a

9. RESEARCH DESIGN AND METHODS

This is a 6-week un-blinded, 2-arm randomized (1:1) controlled clinical pilot study. The overarching objective of this study is to determine the acceptability and feasibility of an acceptance and commitment therapy (ACT) intervention for the management of chronic pain adapted to aPLWH. To accomplish this objective this project will:

- 1) Train lay personnel to perform ACT to determine feasibility of this approach for future implementation,
- 2) Conduct audio recorded, uncontrolled group ACT in aPLWH to generate participant feedback and questionnaire data to inform ACT adaption with the assistance of a steering committee, and
- 3) Conduct an audio recorded, pilot randomized controlled trial (RCT) evaluating the acceptability of adapted ACT compared to pain education.

[figure not shown]
Due to concerns about COVID-19 the study procedures can be conducted remotely using Zoom teleconference services.

At completion of this project we expect to have successfully trained lay personnel to perform group ACT, adapted ACT from quantitative and qualitative data collected from an uncontrolled study of group ACT, and determined whether ACT is acceptable and feasible as an intervention in aPLWH. These expected outcomes may benefit other aging populations with chronic pain that are enriched for psychosocial co-morbidities such as persons who inject drugs, the socioeconomically disadvantaged, and racial or gender minorities. This proposal is aligned with the Office of AIDS Research High Priorities to better understand “HIV-associated comorbidities” which includes pain and to “Reduce Health Disparities in treatment outcomes of those living with HIV/AIDS” and with the National Pain Strategy to “expand investment … in the development of safe and effective pain treatments.”

Research Design and Procedures:

For AIM 1 Training of Lay-personnel in ACT: [name] will train [name] (a retired nurse) and [name] (a substance abuse counselor) in the performance of ACT based on procedures in which non mental health providers have been taught to perform psychological interventions (66-71). Training will use [name] previously developed therapist and client manuals of ACT for chronic pain. This will include an initial 8-hour introduction to ACT followed by weekly 1 hour meetings using the manual to guide case-based scenario training. This amount of preparation is well within the range provided to non-mental health professionals in previous studies of manualized psychotherapy. The final phase of ACT therapist training will take place in the field during Aim 2. [name] will listen to audio recordings of 20% of ACT sessions and meet weekly with ACT counselors to assist with

Figure 2. Study Schema

Legend

~ Study participant informed consent @ Baseline demographics + Pain and Psychosocial Co-morbidity Assessments

*Short telephone or in-person interview about ACT experience

#Focus group

++Acceptability and Pain Assessments

+++Acceptability, Pain and Psychosocial Co-morbidity Assessments

troubleshooting, provide expertise, and ensure fidelity. I will be present through training and at 20% of ACT and education sessions to experientially learn these processes. The ACT therapist trainer and ACT trainees will be complete recorded guided interviews after completion of training.

For AIM 2: Uncontrolled group ACT for Chronic Pain in aPLWH: Ten aPLWH will be recruited for 6 weeks of 2-hour group ACT using previously developed ACT for chronic pain manuals developed for therapists and clients by [name] (Table 2). All sessions will be audio recorded for future analysis. Following each session participants will undergo recorded 10 minute short interview on aspects of the class they liked most and least. These surveys will employ open-ended questions about program content. Participants will undergo baseline demographics and questionnaires about pain and psychosocial co-morbidities (see assessments) to inform generation of open-ended questions and development of a focus group guide. Data from participant feedback and questionnaires will be presented to the steering committee to assist with development of the focus group guide. Participants will complete follow up questionnaires and guided interview questions 3, 6, and 12 months after completion of the group sessions to assess long-term use of ACT.

Table 2: Session Intervention Content

Session	ACT	Take Charge of Your Pain
1	Letting Go	Things to Know about Pain
2	Values	Relaxation
3	Cognitive Defusion	Imagery
4	Mindfulness	Activity Pacing
5	Commitment	Sleep Tips
6	Moving Forward	Dealing with Pain Flare-Ups
7	Practice/review	Review
8	Practice/review	Review

For AIM 2 Adaption of ACT: Following the final group session, a 1-3 hour long focus group will be performed to obtain suggestions for program modification. The focus group will be audiotaped and responses transcribed, categorized and summarized and distributed to members of the study's steering committee which will then meet to review and adjudicate suggested ACT adaptations. Adoptions will

be incorporated into new therapist and client manuals and further training will be provided to ACT therapists for the performance of adapted ACT.

For AIM 3 Acceptability and Feasibility of Adapted ACT Intervention: Forty persons will be randomized to either group adapted ACT or group education. In anticipation of ~15% early discontinuation or lost to follow up, we plan to recruit 50 participants overall. All sessions will be audio recorded for future analysis. Adapted ACT will be provided by ACT therapists in weekly 2-hour group (8-10 persons per group) sessions for the 6 weeks of the intervention and will include brief review of at-home practice assignments, introduction of new material and end with assigned at-home practice exercises. Participants randomized to control will also participate in 2-hour 6 weeks group sessions (8-10 persons) using the “Take Charge of Your Pain” handbook developed by Investigators at the Weill-Cornell Translational Research Institute for Pain in Later Life (Table 2). All sessions will be audio recorded for future analysis. Study participants will complete assessments at baseline, week 3 (midpoint) and week 6 (endpoint). Following completion of study we will assess for persistence of ACT activities and practices by a short telephone follow up. Participants may come to the AVRC for an in person discussion but this will not receive monetary compensation.

Remote Engagement of Study Participants

To ensure safety of participants (who are all older adults with the co-morbidity of HIV) during COVID-19 and respect the “shelter at home” state-wide order this aim will be performed 100% virtually. The protocol specifically has been adapted to include

- 1) over the phone consent. This is a minimal risk study and with COVID-19 the risk of an in-person evaluation greatly outweighs the potential benefit.
- 2) Questionnaires to be completed via a) online through REDCAP mechanism that provides a link and password to allow participants to securely complete questionnaires or b) complete paper questionnaire mailed to participant with stamped envelope for return with only the study ID on papers to protect participant privacy
- 3) Online group meetings using Zoom with password to prevent hackers.
- 4) Compensation provided either using an electronic gift card or a script mailed to the study participant.

Aim 3 substudy: An additional substudy involving two to ten participants will also be performed with the intent in better understanding the relationship between older age, HIV, San Diego as a border town and access to prescribed and non-prescribed medications used for pain. This was originally designed as a focus group, but will now be performed using individual interviews in response to COVID-19.

Assessments: Participants will complete surveys asking about demographic (age, gender, race/ethnicity, education, etc.) and HIV (risk factor, duration of HIV infection, CD4 T cell counts both current and nadir, HIV viral loads, and self-reported ART adherence) factors and montreal cognitive assessment test. Chronic pain diagnoses, medications and non-pharmacologic methods used for pain and the duration of pain will also be collected from participants. Treatment satisfaction will be determined as measured by the Client Satisfaction Questionnaire (CSQ)(72, 73) and The Group Questionnaire at midpoint and intervention end. Treatment expectations will be determined as measured by the Treatment Expectations Questionnaire at week 0 and intervention end. Pain assessments will include change in the Brief Pain Inventory (BPI) Interference subscale and Pain Self Efficacy Questionnaire (PSEQ) from week 0 to 8(74) , the Patient Reported Outcomes Measurement Information System (PROMIS) pain behavior and pain interference questionnaires, measures of physical function using the Short Physical Performance Battery (SPPB) (75) and quality of life using

EuroQol(76). Lastly co-morbidities proposed to impact the pain experience in HIV will be evaluated: stress (Perceived Stress Questionnaire(77)), loneliness (UCLA Loneliness Scale(78)), depression and anxiety (Patient Health Questionnaire-9 and GAD-7(79, 80)), past trauma (Stressful Life Events Screening Questionnaire (81)), social isolation (Friendship scale(82)) stigma (HIV-Stigma scale(83)). Acceptance and action questionnaire, depression and anxiety (Patient Health Questionnaire-8(79) to avoid positive questions about active suicidality given insufficient capacity to immediately address that in the research setting), profile of mood states questionnaire, wisdom questionnaire and substance use (Alcohol, Smoking, and Substance Involvement Screening Test(84)).

Table 1: Step 1 Unadapted ACT Schedule of Events

	Pre study	Wk 0	ACT Intervention								End of Step 1
			1	2	3	4	5	6	7	8	
Training of lay personnel in ACT	X										
Informed Consent	X										
Refusal Survey	X	X									
Demographics/Medical History	X										
Pain Assessments	X										
Psychosocial Co-morbidities	X										
Telephone call about ACT experience			X	X	X	X	X	X	X	X	
Focus group											X
*IC-informed consent, Wk - week											

Table 2: Step 2 Adapted ACT Schedule of Events

	Pre-study	Wk 0	ACT Intervention						End of Step 2	Follow up	
			1	2	3	4	5	6		3 mo	6 mo
Study Steering Committee	X										
Adapt ACT to HIV	X										
Informed Consent	X										
Refusal Survey	X										
Demographics/Medical History	X							X			
Pain Assessments	X							X			
Psychosocial Co-morbidities	X							X			
Acceptability Assessments							X	X			
Pain Assessments							X	X			
Telephone call about ACT persistence										X	X
Selected Treatment Survey						X					

Step 1 (Un-adapted ACT)

Screening Assessment (Week 0)

A PID will be assigned to each patient screened for the study. PID's should not be reassigned even if patient fails to enter the study. The PID must be included on every CRF and patient blood sample. Each site must maintain a master list of PID's in a central location. The patient registration and inclusion/exclusion CRF must be completed on the online system.

Screening will be conducted by [name], or another trained member of the study team and will include medical history, confirmation of HIV test results, evaluation of inclusion/exclusion criteria, and signing of study consent form.

Patients who meet the study eligibility but decline to participate will be offered participation in a brief refusal survey. Patients who verbally consent to participate in the refusal survey will be administered the questionnaire in written or verbal format.

Entry Evaluations

At study entry baseline surveys will be collected using paper CRF or web-based computer assisted system (to view baseline survey see Appendix III). The computer assisted system will allow private completion of questionnaires without concern that clinic or study personnel can view the subjects responses in order to encourage candor. Participants will undergo baseline demographics and questionnaires about pain and psychosocial co-morbidities to inform generation of open-ended questions and development of a focus group guide.

Data Abstraction

It is expected that subjects will not remember exactly their recent medical history. We will abstract HIV VL, CD4, CD4 nadir, estimated date of diagnosis, ART history, and Veterans Aging Score.

Telephone or in Person Feedback from Each Session

Within 48 hours of the session each participant will be contacted by [name] or another trained member of the study team and will inquire about the experience of each individual. This will include aspects of the class they liked most and least. These surveys will also employ open-ended questions about program content.

Long-Term Follow Up

Each participant will be contacted via telephone 3, and 6 months after completion of the group ACT sessions by [name] or another trained member of the study team and will inquire about persistence of ACT practices and strategies participants recommend for ongoing use of ACT. Specifically we will ask if they are continuing ACT practices.

Step 2 Adapted ACT RCT

Screening Assessment (Week 0)

Screening will be identical to Step 1.

Entry Evaluations and Randomization

Subjects will be randomized (1:1) to ACT versus education control. A total of 20 subjects (10 per arm) will be randomized and followed for the duration of the six weeks of the intervention and control. Once ten participants are enrolled into one group that will start that adapted ACT intervention will start. At study entry baseline surveys will be collected using paper CRF or web-based computer assisted system (to view baseline survey see Appendix III) similar to Step 1.

On-Study Evaluations

Study specific follow-up visits for each subject will be kept to a minimum in order not to bias the outcome of lost to follow up. Participants will undergo pain and acceptability questionnaires at week 3 (Appendix VI). These will be repeated along with psychosocial co-morbidity questionnaires at week 8. Participants

will be provided \$20 for completion of baseline assessments, \$30 for midpoint and \$50 for endpoint assessments.

Instructions for Evaluations

Documentation of HIV

Documentation of HIV-1 infection will be confirmed by reviewing a positive test from any licensed screening antibody test, such as ELISA, and confirmed by a second antibody test, such as Western blot, or detectable plasma HIV-1 RNA at any time prior to study entry. If an ELISA or Western Blot is not available, HIV infection may be documented by two HIV RNA values \geq 2000 copies/mL, drawn at least 24 hours apart. The RNA assays should have been run at CLIA approved laboratory or equivalent.

Medical and Laboratory History

At screening, a medical history will be obtained and must be recorded in the source documents. The medical history should include any previous HIV-related diagnoses, pain, malignancies, and AIDS-defining events which will be recorded on the electronic CRF. History will include date of HIV diagnosis, date of last HIV clinic visit (for those returning to care), antiretroviral (ARV) history (if any), concomitant medical conditions, substance use history.

Medication History

At screening, a medication history (only of those taken within the last 30 days prior to entry) with actual or estimated start and stop dates should be obtained and recorded in the source documents and the concomitant medication CRF, including:

- ♦ All prescription medications, including medications taken for the treatment or prophylaxis of opportunistic infections.

Non-prescription medications.

Alternative therapies and/or dietary supplements.

Allergies to any medications and their formulations must be documented.

Concomitant Medications

At baseline concomitant medications of interest taken since the last visit will be recorded in the source documentation and entered into the concomitant medication log CRF.

Antiretroviral and Pain Medication Modifications

All modifications of antiretroviral and pain medications will be recorded on the CRF's at the baseline, week 3 and 6 data extractions for Step 2: including initial doses, patient-initiated interruptions, modifications, and permanent discontinuations. These medications will also be reviewed and confirmed at the annual study visits.

Clinical Assessments

Height and Weight

Height and weight should be documented at study entry and weight documented at annual visits.

Immunologic and Virologic Studies

Nadir CD4+ T-Cell Count

The subject's prior nadir CD4+ cell count (absolute value and date) should be documented during screening and, when possible, a copy of nadir CD4+ cell count report should be included in the source

document. If this documentation is not available, then subject recollection will suffice. For Subjects who do not know the exact nadir value and for whom there is no source documentation, then recall of the categorical nadir (e.g., < 50, < 100, < 200 cells/mm³) will suffice.

CD4/CD8 and HIV-1 RNA

At baseline, the past 12 months of CD4/CD8 count and percentage and HIV-1 RNA will be recorded. The results will be obtained via chart extraction.

Antiretroviral resistance testing

If patients have had an antiretroviral resistance test during routine care, that data will be collected via chart abstraction.

Clinical Management Issues

This is a minimal risk study. No toxicities are anticipated a no treatment or invasive procedures are being performed as part of the study. However possible risks include:

Emotional distress

This behavioral intervention bring up past trauma or experiences that cause emotional distress. A highly experienced psychologist with post traumatic stress disorder experience is the Co-investigator of this study and will assist in triage as needed. In addition, the Owen Clinic has embedded psychiatrists that are available daily for emergency evaluations and will be utilized if any study personnel raise concerns about the state of participants. Emergency room evaluations will be encouraged if distress occurs after hours. Of note the AntiViral Research Center has a 24 hour physician on call to assist with triage of participants in various studies.

Selected Pain Interview

Participants will be asked to complete a short survey concerning their pain and pain treatment methods. These surveys will take place during the second (2nd) Arm 2 study visit.

Criteria for Discontinuation

- Subject requests to withdraw participation
- Primary care provider requests for subject withdrawal based on the provider's belief that study participation is no longer in subject's best interest
- Medical provider belief that the patient has life threatening clinical condition
- By the discretion of the site IRB, NIH or investigator

Statistical Considerations

This section briefly describes the planned statistical analysis. The statistical Analysis Plan (SAP) provides details. If the language in this section differs from the language in the SAP, the SAP takes precedence.

Analytic Plan: [name] and her team will lead all statistical analyses for this study. For the RCT we will obtain descriptive statistics to compare baseline characteristics between study arms (ACT versus pain education). Categorical variables will be analyzed using Fisher's Exact Test and continuous variables using Wilcoxon Rank Sum Test. To determine acceptability of group ACT, we will use the CSQ at endpoint of the intervention as the primary outcome. This is a pilot study, but we will utilize a superiority

study design, and incorporate an intent-to-treat (ITT) approach to analyze the outcome data. We will employ multivariable logistic regression analysis to study the association between clinical (duration of HIV infection, nadir CD4, BPI), demographic (i.e., age, sex, duration of HIV infection, nadir CD4), and psychosocial factors (i.e., substance use, loneliness) and intervention arm adjusting for baseline demographic and clinical characteristics. Variables significantly associated with treatment groups and outcome ($p < 0.10$) including appropriate interaction terms, will be included in the final multivariable logistic regression model as covariates. CSQ at midpoint and proportion of sessions attended will be evaluated in sensitivity analyses. The study procedures can occur in person or remotely. We will statistically evaluate this process and compare group cohesion scores between persons who attend live (if feasible) and remotely.

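### Both arms are treated in groups of 8-10, but the endpoint-CSQ superiority comparison names only individual-level methods, and the two stated trial sizes imply different numbers of groups per arm

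*Combined protocol and SAP*

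**What the plan says.** Section 9 (Research Design and Methods, For AIM 3) sets the size and the delivery: "Forty persons will be randomized to either group adapted ACT or group education". In the active arm, "Adapted ACT will be provided by ACT therapists in weekly 2-hour group (8-10 persons per group) sessions". Control participants "will also participate in 2-hour 6 weeks group sessions (8-10 persons"). The same paragraph plans to recruit 50, allowing for about 15% early discontinuation or loss.

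Section 9 (Step 2 Adapted ACT RCT, Entry Evaluations and Randomization) states 1:1 randomisation of subjects but gives another size: "A total of 20 subjects (10 per arm) will be randomized". On group formation it says: "Once ten participants are enrolled into one group that will start that adapted ACT intervention will start".

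The Analytic Plan under Statistical Considerations says "we will use the CSQ at endpoint of the intervention as the primary outcome" and continues "This is a pilot study, but we will utilize a superiority" design, analysed by intention to treat. The methods it names are Fisher's exact test and, for "continuous variables using Wilcoxon Rank Sum Test" (both in the sentences on baseline comparisons), and then multivariable logistic regression with participant-level covariates. Group cohesion scores are to be compared between live and remote attenders. The section defers detail to a statistical analysis plan that takes precedence.

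**The concern.** CSQ measures satisfaction with a service that 8-10 people receive together over six weekly sessions. Members of a group share a leader, a dynamic and a set of incidents, so their scores may resemble each other. The protocol itself treats group experience as relevant: it plans a cohesion analysis and restricts language partly because of group dynamics. Neither step carries group into the CSQ comparison.

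With so few groups, one well-liked or poorly liked group could be read as ACT being more or less acceptable than education. Acceptability is what the pilot exists to measure, and the plan frames that comparison as superiority. With one group per arm, a group effect and a treatment effect cannot be told apart by any model.

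**Working it through.** **The plan's own figure.** Forty randomised with 15% loss gives 40/0.85 = 47.06, rounded up to 48; the stated 50 agrees to within two people. No power calculation is given, so none is disputed.

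**Number of groups.**
- 40 randomised: 20 per arm, which is two groups of 10 per arm.
- 20 randomised: 10 per arm, which is one group per arm.
- 50 randomised (a possible reading of the recruitment target): 25 per arm, which fits three groups of 8-9.

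**Inputs from the documents.** Group size 8-10; 40 randomised; about 15% loss.

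**Assumptions.** Two-sided alpha 0.05; normally distributed CSQ; ICC of 0.01, 0.05 or 0.10; for logistic regression, CSQ cut at the median or with 70% satisfied. The documents give none of these.

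**Standard error.** The design effect is 1 + (m - 1) x ICC. With m = 10 it is 1 + 9 x 0.01 = 1.09, 1 + 9 x 0.05 = 1.45 and 1 + 9 x 0.10 = 1.90. The true standard error is the square root of that times the individual-level one: 1.04, 1.20 and 1.38.

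**Type I error, by simulation with no true effect, two groups per arm, groups ignored:**

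| Analysis | ICC 0 | 0.01 | 0.05 | 0.10 |
|---|---|---|---|---|
| Wilcoxon on CSQ, 10 per group | 0.05 | 0.06 | 0.10 | 0.15 |
| Unadjusted logistic, 10 per group | 0.04 | 0.045 | 0.07 | 0.10 |
| Wilcoxon, 34 analysed | 0.05 | 0.06 | 0.09 | 0.135 |

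The last row is 40 x 0.85 = 34, or 34/4 = 8.5 per group (8-9 people). The logistic test starts below nominal at this size, which hides part of the inflation. Its figures also depend on the cut: splitting at the observed sample median gives about 0.03 instead of 0.045 at ICC 0.01 with groups of 10.

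**One group of 10 per arm.** An individual-level t test has error of about 0.058, 0.106 and 0.164 at the same ICCs. There is no within-arm replication of groups from which to correct it.

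**Width of an interval that respects groups.** A t interval on group means has 2 degrees of freedom with two groups per arm (critical value 4.30, against 2.02 at 38 degrees of freedom). Simulated mean half-widths over ICC 0.01 to 0.10 are:
- two groups of 10 per arm: 1.26 to 1.66 SD;
- three groups of 8 per arm (close to 50 randomised): 0.78 to 0.98 SD;
- individual-level analysis that ignores groups: about 0.6-0.7 SD.

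The group-mean interval with two groups per arm covers at 0.95.

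**The case against.** **A separate analysis plan may deal with grouping.** This stands as a limit. A reader might infer that the trial's final analysis ignores groups. The documents do not show that; they show only that the text available does not say how group enters.

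**No CSQ arm test is clearly defined.** Also true. Wilcoxon is named for baseline variables, the logistic sentence speaks of associations with intervention arm, and no CSQ cut is given. The error rates above therefore describe what the named methods would do if applied to CSQ. A reader might conclude that the primary result will be badly inflated. Without an ICC or a defined test that cannot be said, and at ICC 0.01 the effect is negligible.

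**The number of groups is not settled.** Agreed. If 50 are randomised in three groups per arm, the cost in width is much smaller. The study schema is a figure that could not be read and may give the number.

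**Who leads the education groups is not stated in the readable text.** A reader might count this as a fault in the plan. It should not be: names and some pages were removed, so the information may be there. The possible confounding of leader with arm is worth noting, but it is not evidence of an error.

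**It is a pilot with acceptability as its outcome and no stated power.** That lowers the stakes and argues against adding participants. It does not justify a superiority conclusion from about four groups.

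**Conclusion.** The point holds in conditional form. Grouped delivery in both arms, a superiority comparison of endpoint CSQ and exclusively individual-level methods are all in the text. If CSQ is positively correlated within groups and the named kind of analysis is used, uncertainty is understated. From an ICC of about 0.05, a nominal 5% test runs at roughly 7-10%, and at 0.10 at roughly 10-15% (lower figure logistic, upper Wilcoxon; two groups of 10 per arm). These sizes rest on an assumed ICC, alpha, outcome distribution and CSQ cut.

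The conflict between 40 and 20 randomised does not depend on any of those assumptions. It decides whether an inferential comparison is possible at all, because one group per arm confounds group with arm completely. The change is worth making before analysis, but it is not a reason to redesign the pilot.

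**What to change.** 1. Reconcile the number randomised between the Aim 3 text and the Step 2 text, and state the planned number of groups per arm.
2. Present the endpoint-CSQ arm difference as a pilot estimate and not as a superiority conclusion, with CSQ shown by treatment group. With at least two groups per arm, give an interval that allows for group with small-sample degrees of freedom (group means or a mixed model, at the statistician's choice) beside the individual-level result. With one group per arm, keep the comparison descriptive.
3. Keep treatment-group and leader identifiers in the dataset. Note that leader may be confounded with arm if the same people lead every group in an arm; no group-level interval removes that.

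**Cost.** Two data fields and some wording, but also the superiority claim and a wider interval: a mean half-width of about 1.3-1.7 SD with two groups per arm, or about 0.8-1.0 SD with three, against about 0.6-0.7 SD when groups are ignored. The methods are imperfect with so few groups. Across the settings simulated with two groups of 8 or 10 per arm, the group-mean interval is by chance narrower than the individual-level one in roughly 10-18% of trials, and a random-intercept model sets the group variance to zero in 37-59%. That is why both results should be shown. For a pilot that states no power, this is an acceptable price.
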